6.2. Discussion of Study Design

Congruent to Draft Guidance “*Clinical Immunogenicity Considerations for Biosimilar and Interchangeable Insulin Products*”, the Sponsor believes the aforementioned comparative analytical assessment demonstrates NKF-INS(A) is highly similar to EU-NovoRapid®, and US-NovoLog® and there is no residual uncertainty regarding immunogenicity. Therefore, in addition to the comparative analytical assessments, the Sponsor plans to conduct one Phase 1 study to demonstrate PK similarity to reference products to provide a totality of evidence for biosimilarity for licensure.

The design of the study was chosen as both FDA and European Medicines Agency recognize the clamp technique as the most reliable method for qualifying the PK and PD proprieties of a novel biosimilar. Clamp technique is used to rapidly attain the required blood glucose levels and maintain it at target levels ([Heinemann et al, 2023](#)).

6.3. End of Study

A participant will have fulfilled the requirements for study completion if/when the participant has completed all three treatment periods and the end of study (EOS) visit within 2-11 days after last administration of the study drug.

The EOS is defined as the date of the last visit for the last participant in the study/last scheduled procedure shown in the schedule of assessments ([Table 3](#)).

6.4. Criteria for Early Study Termination

The Sponsor reserves the right to close a study site or terminate the study at any time for any reason. Study sites will be closed upon study completion. A study site is considered closed when all required documents and study supplies have been collected and a study site closure visit has been performed.

The Investigator may initiate study site closure at any time, provided there is reasonable cause and sufficient notice is given in advance of the intended termination.

Reasons for the early closure of a study site by the Sponsor or Investigator may include but are not limited to:

- Failure of the Investigator to comply with the protocol, requirements of the Institutional Review Board (IRB)/Independent Ethics Committee (IEC) or local health authorities, the Sponsor's procedures, or ICH GCP guidelines, or contractual agreement.
- Inadequate recruitment of participants by the Investigator.
- Discontinuation of further development of NKF-INS(A).

The IRB/IEC and regulatory authorities will be informed about the reason and time of the termination according to applicable laws and regulations. If the study is terminated prematurely, Investigators will inform their participants.

7. SELECTION OF STUDY POPULATION

7.1. Inclusion Criteria

Individuals must meet all of the following inclusion criteria to be included in the study:

1. Signed and dated informed consent obtained before any trial-related activities. Trial-related activities are any procedures that would not have been done during normal management of the participant.
2. Healthy male participants.
3. Age between 18 and 50 years, both inclusive.
4. Body Mass Index between 18.5 and 29.0 kg/m², both inclusive.
5. Body weight \geq 50 kg.
6. Fasting plasma glucose concentration \leq 5.5 mmol/L at screening.
7. Considered generally healthy upon completion of medical history, physical examination, vital signs, ECG, and analysis of laboratory safety variables, as judged by the Investigator.
8. Willing and able to comply with scheduled visits, treatment plan, clinical laboratory tests, and other study procedures including lifestyle considerations.
9. Participants must agree to use condoms during sexual intercourse. Additionally, female partners of male participants should use highly effective contraception. All contraceptive measures apply from screening until 90 days after study treatment. Male participants must refrain from donating or banking sperm for 90 days after administration of study treatment.
10. Have competence in speaking, writing, and comprehending the local language(s) where the study is conducted.

7.2. Exclusion Criteria

Individuals will be excluded from participation if they meet any of the following criteria:

1. Positive for human insulin antibodies at Screening.
2. Are currently enrolled in or have discontinued within 3 months or 5 half-lives (whichever is longer) of any investigational drug or device or are concurrently enrolled in any other type of medical research study and judged not to be scientifically or medically compatible with this study.
3. Have known allergies to insulin, its excipients, or related drugs or have history of relevant allergic reactions of any origin.
4. History of diabetes mellitus; episodes of hypoglycemia in the anamnesis; any history of insulin use for treatment purposes.

5. Have known allergies to insulin, its excipients, or related drugs or have history of relevant allergic reactions of any origin.
6. Have clinically relevant history of current cardiovascular, respiratory, hepatic, renal, gastrointestinal, endocrine, hematological, or neurological disorders capable of significantly altering the absorption, metabolism, or elimination of drugs; of constituting a risk when taking the study drug; or of interfering with the interpretation of data.
7. Increased risk of thrombosis, e.g., individuals with a history of deep leg vein thrombosis or family history of deep leg vein thrombosis, as judged by the Investigator.
8. Clinically significant abnormal ECG at screening.
9. Glycemia level ≥ 140.4 mg/dL 2 hours after the glucose load.
10. Show evidence of significant active neuropsychiatric disease.
11. Positive urine drug test at screening and/or evidence of current use of known drugs of abuse or have a history of use within the past year.
12. Show evidence of an acute infection with fever or infectious disease at the time of enrollment.
13. Show evidence of human immunodeficiency virus (HIV) infection and/or positive human HIV antibodies at screening.
14. Have positive test results for hepatitis B surface antigen (HBsAg), immunoglobulin M (IgM) antibody to hepatitis B core antigen (anti-HBc), or hepatitis C virus (HCV) antibodies at screening.
15. Intend to use over-the-counter medication within 7 days or prescription medication within 14 days prior to dosing (apart from vitamin/mineral supplements, occasional paracetamol, thyroid replacement).
16. Have donated blood or had a blood loss of 450 mL 3 months prior to study enrollment.
17. Have an average weekly alcohol intake that exceeds 21 units per week or is unwilling to stop alcohol consumption from 48 hours prior to each dosing until being discharged from the CRU.

7.3. Rescreening

Screen failures are defined as participants who consent to participate in the clinical study but are not subsequently entered into the study. A minimal set of screen failure information is required to ensure transparent reporting of screen failure participants to meet the Consolidated Standards of Reporting Trials publishing requirements and to respond to queries from regulatory authorities. Minimal information includes demography, screen failure details, eligibility criteria, and any serious adverse event (SAE).

Individuals who do not meet the criteria for participation in this study (screen failure) may be rescreened only once, at the discretion of the Investigator.

The participant must be reconsented and a new screening number will be assigned. Also, a new informed consent form (ICF) must be signed if updates have been made since signing of the first ICF.

7.4. Study Withdrawal, Removal, and Replacement of Participants

Participants may withdraw from the study at any time with or without reason. The Investigator also has the right to discontinue or terminate participants from the study in the event of concomitant disease, AEs, or any reason that would benefit the participant (see Section [8.4](#)).

If a participant withdraws from the study for any reason, the study site must immediately notify the clinical monitor. The date and the reason for study discontinuation must be recorded in the electronic case report form (eCRF). Participants who discontinue early, irrespective of the reason for discontinuation from the study, will be asked to complete the EOS assessments at the time of the participant's withdrawal, as outlined in the schedule of assessments ([Table 3](#)).

If a participant withdraws from the study, he may request destruction of any samples taken and not tested, and the Investigator must document this in the site study records.

Additionally (as described in Section [6.4](#)), the Sponsor may stop the study at any time for safety, regulatory, legal, or other reasons aligned with GCP. This study may be terminated at the discretion of the Sponsor or any regulatory agency. An Investigator may elect to discontinue or stop the study at his or her study site for any reason, including safety or low enrollment.

7.4.1. Replacement of Participants

Participants who sign the ICF and are randomized but not treated may be replaced at the discretion of the Sponsor.

8. TREATMENTS

A list of study treatments used in this study is provided in [Table 2](#).

Table 2 Study Treatments

Agent	Use
NKF-INS(A)	Investigational agent
US-NovoLog® and EU-NovoRapid® Flex Pen	Indicated to improve glycemic control in adults and children with diabetes mellitus

Source: [NovoLog® United States Prescribing Information \(USPI\)](#); [NovoRapid Summary of Product Characteristics](#)

8.1. Study Treatment Description

NKF-INS(A), US-NovoLog® and EU-NovoRapid® is intended to be administered as a 0.3 U/kg single dose SC in the perumbilical area.

[figure not shown]
US-NovoLog® and EU-NovoRapid® will be supplied by Novo Nordisk, Plainsboro, NJ, US.

NKF-INS(A) is a clear and colorless solution.

NKF-INS(A) is supplied in a disposable pen (with cartridge) containing 300 U/3mL; 1 mL solution contains 100 units of NKF-INS(A), equivalent to 3.5 mg. The disposable pen syringe device is a BD Vystra Disposable Pen sourced commercially ([Figure 2](#)).

[figure not shown]
Figure 2 Investigational Product Description

BD Vystra™ Disposable Pen

[figure not shown]

US-NovoLog® and EU-NovoRapid® is supplied in a disposable pen syringe containing 300 U/3mL ([NovoLog® United States Prescribing Information \(USPI\)](#); [NovoRapid Summary of Product Characteristics](#)[SmPC]); 1 mL solution contains 100 units of insulin aspart equivalent to 3.5 mg. The disposable pen is a proprietary device with a NovoFine needle ([Figure 3](#)).

Figure 3 Control Treatment

NovoFine® needle

8.1.1. Preparation, Handling, and Disposal

The preparation of NKF-INS(A), US-NovoLog® and EU-NovoRapid® will be conducted in accordance with the Pharmacy Manual.

Procedures for proper handling and disposal should be followed in compliance with the SOPs of the site.

8.1.2. Product Labeling and Packaging

NKF-INS(A), US-NovoLog® and EU-NovoRapid® will be labeled to meet country-specific regulatory requirements.

Refer to the Pharmacy Manual for packaging and labeling information.

8.1.3. Administration

NKF-INS(A), US-NovoLog® and EU-NovoRapid® will be administered as a single dose via the SC route (refer to Section 8.2). Device-related events or complaints should be reported to the Sponsor in accordance with the Pharmacy Manual.

8.1.4. Storage

Refer to the Pharmacy Manual for information regarding storage, handling, and administration of NKF-INS(A), US-NovoLog® and EU-NovoRapid®.

Before opening (unpunctured), NKF-INS(A) should be stored at 2 °C to 8 °C (36 °F to 46 °F) and protected from heat and light until the time of use. The drug product must not be frozen or placed adjacent to the refrigerator cooling element.

During use (punctured), NKF-INS(A) should be stored below 30 °C (86 °F) for up to 28 days and should not be exposed to excessive heat or sunlight. Do not freeze and do not draw into a syringe for later use. Pen cap should be kept on the pen in order to protect from light.

Always remove and discard the needle after each injection of NKF-INS(A) pen. Pens are considered single use.

The shelf life during use for US-NovoLog® and EU-NovoRapid® is 28 days when stored below 30 °C (86 °F). The unpunctured disposable pen can be used until their expiry date if stored at 2 °C to 8 °C (36 °F to 46 °F). NKF-INS(A) is being studied on an ongoing stability program and is tested at regular intervals to establish shelf life.

8.2. Dosage Schedule

Upon admission to the CRU on Day -1, participants will be randomized on Day 1 to one of six treatment sequences in a 1:1:1:1:1:1 ratio, receiving a single SC dose of 0.3 U/kg administration of one of the three study drugs on each dosing day.

The insulin products will be administered using an euglycemic glucose clamp at a targeted blood glucose concentration. The euglycemic glucose clamp will be conducted using a clamp technique. The glucose clamp device will manually adjust the infused GIR to maintain the target blood glucose concentration based on the actual measured blood glucose concentration and the degree of variability in the previous minute.

Blood samples will be collected at pre-specified intervals before and up to 12 hours after dosing for measurement of blood glucose, serum insulin, and C-peptide.

Participants will visit the study site for 3 single-dose periods with specified washouts (3-14 days between treatment periods 1 and 2; and 5-21 days between treatment periods 2 and 3). The entire duration of the study will be a maximum of 11 weeks.

8.3. Measures to Minimize Bias: Study Treatment Assignment and Blinding

8.3.1. Method of Study Treatment Assignment

Participants will be assigned a screening identification (ID) number when providing informed consent. A participant ID will be provided on Day -1. A participant ID consists of a site ID and a participant number that uniquely identifies each participant.

On Day 1, participants will be randomly allocated to study treatment sequence according to a pre-specified randomization scheme prepared by an independent statistician (refer to Section 8.2).

8.3.2. Blinding

All participants, Investigators, and study personnel involved in the conduct of the study will be blinded to treatment assignment with the exception of unblinded statistician, programmer, pharmacists, and drug administrator.

Because study drug and comparator differ slightly in appearance, the study drug will be prepared by an unblinded pharmacist and administered by an unblinded administrator, while the participant is blindfolded. The used pen will be returned to the packaging and reconciliation will be completed by the unblinded pharmacist.

The unblinded study personnel will not participate in study procedures or data analysis prior to unblinding of the study data.

The following controls will be employed to maintain the double-blind status of the study:

The randomization list will be kept within the Clinical Data Management System and role-based access will prevent any unauthorized personnel from accessing the blinded information. The pharmacist will have access to the randomization list for dispensing purposes.

- To manage the participant's condition in case of a medical emergency, the Investigator will be able to break the blind for a specific participant, using the Clinical Data Management System, to know whether a participant received NKF-INS(A), US-NovoLog® and EU-NovoRapid®. In order to break the blind, the Investigator will have to provide a reason for doing so. All relevant data including the responsible individual, the date, the time, and the reason for breaking the blind will be captured electronically within audit trail of the Clinical Data Management System. The Sponsor will be informed in case of unblinding.
- Extra measures (where relevant) will be put in place to maintain the blind during dosing, e.g., blindfolding of participants, presenting the study treatments as identical in appearance where possible, double-blind labelling, unblinded personnel to administer study treatment.

8.4. Treatment Modifications and Discontinuations

Dose reductions and adjustments are not permitted; any dose reductions and adjustments that occur will be recorded and considered protocol deviations.

Delays and omissions of study treatment administration because of medical or nonmedical reasons are not permitted. All delays and omissions of study treatment that occur during the study will be recorded and considered protocol deviations.

A participant may be discontinued from the study at any time for reasons including, but not limited to, the following:

- AE and/or SAEs in the judgment of the Investigator that may prevent the participant from continuing participation in the study.
- Participant withdrawal of consent (at any time, a participant's participation in the study may be terminated at their request).
- On the basis of the Investigator's clinical judgment.
- General or specific changes in the participant's condition that render them ineligible for further treatment according to the inclusion/exclusion criteria.
- Participant fails to adhere to the protocol requirements (e.g., study treatment noncompliance).
- Lost to follow up: the participant stopped coming for visits and study personnel were unable to contact the participant.

Note: In cases in which the participant is deemed lost to follow up, prior to this designation, the Investigator (or designee) must make every effort to make contact with the participant (e.g., telephone calls, certified letter to the participant's last known mailing address, or local equivalent methods, and efforts to reach the participant's emergency contact). The site will make 3 attempts to regain contact with the participant. These contact attempts must be documented in the participant's medical records.

Any participant who discontinues from the study will be asked to return to the clinic for an EOS visit that includes the assessments as shown in the schedule of assessments ([Table 3](#)). The reason and date for the participant's discontinuation from the study must be recorded in the eCRF.

8.5. Treatment Accountability and Compliance

The pharmacist or other designated individual will maintain records of study drug delivered to the study site, the inventory at the study site, the distribution to and use by each participant, and the return of materials to the Sponsor for storage or disposal/destruction of materials at the study site. These records must include dates, quantities, lot/batch/serial numbers, expiration dates, storage temperature log, and unique code numbers assigned to the study drug and study participants.

Investigators/designee will maintain records that adequately document that the participants were provided with the correct study treatment and reconcile the products received from the drug dispensing center. Investigational product will not be returned to the Sponsor or disposed of until accountability has been fully monitored.

Administration of the study treatment will be supervised by unblinded study site personnel to ensure compliance. An unblinded monitor will periodically review the study records to ensure compliance. Discontinuation for noncompliance is at the Investigator's discretion and is to be noted in the eCRF.

Cases of accidental overdose or medication error, along with any associated AEs, should be reported as described in Section [12.6.2](#).

8.6. Prior and Concomitant Therapy and Other Restrictions During the Study

8.6.1. Prior and Concomitant Medications

Medications taken by or administered to the participant for the period before screening will be recorded in the eCRF as prior medications. Restricted prior therapies include over-the-counter medication within 7 days or prescription medication within 14 days prior to dosing (apart from vitamin/mineral supplements, occasional paracetamol, thyroid replacement, or birth control methods).

Any medication or vaccine (including over-the-counter or prescription medicines, vitamins, and/or herbal supplements) other than NKF-INS(A), US-NovoLog® and EU-NovoRapid® that the participant is receiving at the time of enrollment, or receives during the study, must be recorded in the eCRF as concomitant medications along with:

- Reason for use

- Dates of administration including start and end dates
- Dosage information including dose, regimen, route, and frequency

The participant must be told to notify the investigational site about any new medications taken after administration of the study treatment.

All previous and on study Coronavirus disease 2019 (COVID-19) vaccinations should be recorded in the eCRF.

The Medical Monitor should be contacted if there are any questions regarding prior or concomitant therapy.

8.6.1.1. Permitted Concomitant Medications and Therapies

Other than those medications explicitly prohibited (Section 8.6.1), concomitant medication decisions will be left to the discretion of the Investigator.

8.6.1.2. Prohibited Concomitant Medications and Therapies

Participants must be instructed not to take any medications, including over-the-counter products, without first consulting with the Investigator.

If the participant has received any other investigational drug within 3 months before the administration of study treatment, he will not be eligible for this study.

No prophylactic medication, treatments, or procedures will be administered during the study period, unless at the discretion of the Investigator.

8.6.1.3. Advisory on COVID-19 Vaccination and Risk Assessment

The COVID-19 pandemic is an ongoing pandemic with varying impact at any time in different geographies worldwide (World). It is recommended that participants and their investigators discuss on an individual basis the benefits and risks of COVID-19 vaccination in the context of their prior vaccination history and consider the vaccinations approved by national regulatory agencies, as well as COVID-19 vaccination guidance from scientific and medical associations.

The following recommendations should be considered for the study:

- Participants with prior COVID-19 vaccination may be allowed to enter the study with a washout period of at least 7 days since the last COVID-19 vaccine dose.
- Administration of a COVID-19 vaccine during participation in the study should be documented as a concomitant medication (Section 8.6.1).
- Previous administration(s) of COVID-19 vaccine should be documented in the prior and concomitant medication form.

8.6.2. Other Restrictions During the Study

8.6.2.1. Meals and Dietary Restrictions

For all treatment periods, participants will fast for 10-12 hours prior to dosing and until the glucose clamp procedure is completed, after which participants will receive a meal. There is no restriction on water during the fasting periods of the study. When not in CRU subjects will be encouraged to follow their normal diets. Grapefruit juice is an inhibitor of the CYP3A4 enzyme but CYP3A4 does not play a role in the metabolism of insulin aspart thus it is not mentioned.

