Planned Sample Size	54 healthy male participants are planned to be enrolled in the study to have at least 36 evaluable participants.
Investigational Therapy	NKF-INS(A) administered as a 0.3 U/kg single SC dose in the perumbilical area.
Reference Therapy	EU-NovoRapid® and US-NovoLog®, both administered as a 0.3 U/kg single SC dose in the perumbilical area.

Treatment Duration	The study will consist of a screening period of up to 4 weeks (Days -28 to -1), three treatment periods each consisting of 1-day dose administrations and euglycemic clamp periods (periods 1, 2, and 3) separated by a washout period of 3-14 calendar days between treatment periods 1 and 2, and a washout period of 5-21 calendar days between treatment periods 2 and 3, and a follow-up period of 2-11 days. The entire study duration will be a maximum of 11 weeks.
Pharmacokinetics	Insulin (serum) samples will be collected at 60, 30, 0 minutes pre-dose and 5, 10, 20, 30, 40, 50, 60, 75, 90, 105, 120, 135, 150, 180, 210, 240, 300, 600, and 720 minutes post-dose.
Pharmacodynamics	C-peptide (serum) 60, 30, 0 minutes pre-dose and 5, 10, 20, 30, 40, 50, 60, 75, 90, 105, 120, 135, 150, 180, 210, 240, 300, 600, and 720 minutes post-dose. Blood glucose values will be analyzed pre-dose, every 3 minutes from 0 to 120 minutes, every 5 minutes from 120 to 240 minutes, and every 10 minutes from 240 to 720 minutes post-dose.
Immunogenicity	Not applicable

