Abbreviations: ALP = alkaline phosphatase; ALT = alanine aminotransferase; anti-HBc = antibody to hepatitis B core antigen; aPTT = activated partial thromboplastin time; AST = aspartate aminotransferase; CRU = clinical research unit; ECG = electrocardiogram; EOS = end of study; GGT = gamma-glutamyl transferase; GIR = glucose infusion rate; Hb = hemoglobin; HBsAg = hepatitis B surface antigen; HCT = hematocrit; HCV = hepatitis C virus; HIV = human immunodeficiency virus; IgM = immunoglobulin M; INR = international normalized ratio; MCH = mean corpuscular hemoglobin; MCV = mean corpuscular volume; PD = pharmacodynamic; PK = pharmacokinetic; PT = prothrombin time; RBC = red blood cell; WBC = white blood cell

1 There will be a washout period of 3-14 calendar days between treatment period 1 and 2, and a washout period of 5-21 calendar days between treatment periods 2 and 3.

2 The clamp procedure will be considered as ended if the 20% GIR is on zero (0) and the infusion pump has been stopped or the 12-hour mark is reached. Blood glucose concentration will be measured for 3 consecutive times for safety reasons, after the infusion pump is on zero (0).

3 Sex, race, year of birth, age, and ethnicity.

4 The recorded medical history will be updated, if necessary, at admission to treatment period 1.

5 Participants will be admitted to the CRU approximately 12 hours prior to dosing on Day -1.

6 Randomization will only be done on first sequence.

7 Body weight will be recorded at screening and on Day -1 of all treatment periods. The weight measured on Day -1 of treatment period 1 will be used for dosage calculations of insulin. Height will be recorded at screening only. 8 A full physical examination will include the following: Evaluation for jaundice, pallor (anemia), cyanosis, clubbing, edema and lymphadenopathy; skin evaluation; fundoscopy; ear, nose and throat; cardiovascular assessment; respiratory assessment; abdominal evaluation; musculoskeletal assessment; neurological assessment; other evaluations may be performed as deemed necessary by the Investigator. A full physical exam should be done at screening. A limited symptom-based physical exam may be done at timepoints thereafter.

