18 From 1 hour before study drug administration until 3 hours post-dose, the injection site will be kept at a constant temperature. The time of injection is defined as time zero (0 hour/0 min) and marks the start of the clamp period, which will continue for up to 12 hours or until the GIR is 0 and blood glucose remains stable.

19 The injection site will be assessed at 1 min and 15 min post-dose on Day 1 and at the EOS visit. Reactions to the study drug injection will be documented using a numerical scoring system.

Table 4. Pharmacokinetic, Pharmacodynamic, C-Peptide, and Glucose Sampling Schedule

Sample	Pre-dose (minutes)		Post-dose (minutes)																		
	60	30	0	5	10	20	30	40	50	60	75	90	105	120	135	150	180	210	240	300	600
Insulin (serum)	X	X	X	X	X	X	X	X	X	X	X	X	X	X	X	X	X	X	X	X	X
C-peptide (serum)	X	X	X	X	X	X	X	X	X	X	X	X	X	X	X	X	X	X	X	X	X
Blood glucose			Every 3 minutes											Every 5 minutes				Every 10 minutes			

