13. OTHER ASSESSMENTS

13.1. Euglycemic Clamp Procedure

NKF-INS(A), US-NovoLog® and EU-NovoRapid® will be administered using a euglycemic glucose clamp at targeted blood glucose concentrations. The euglycemic glucose clamp will be conducted using a manual clamp technique, which will continuously monitor the subject's blood glucose and administer GIR to maintain blood glucose close to the target blood glucose concentration. The clamp procedure will be initiated, maintained, and terminated, in accordance with the site SOPs. The participant's blood glucose will be maintained within a pre-defined target window per site SOP and clinical judgment for the participant by manually adjusting the GIR.

Blood samples will be collected at pre-specified intervals before and up to 12 hours after dosing for measurement of blood glucose, serum insulin, and C-peptide as shown in the schedule of assessments ([Table 3](#)).

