### 2.3 Exploratory objectives

- To assess endogenous insulin suppression via C-peptide measurements, which includes both corrected and uncorrected C-peptide concentrations.

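### If a clamp ends before 12 hours, the 600- and 720-minute C-peptide samples can be drawn after a meal, and the SAP has no rule for them

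*Protocol*

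**What the plan says.** Three sets of rules bear on the late samples.

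- **Meal.** Protocol 8.6.2.1: "participants will fast for 10-12 hours prior to dosing and until the glucose clamp procedure is completed, after which participants will receive a meal". The fast is tied to the clamp; no post-dose hour is given and blood sampling is not mentioned.
- **Clamp end.** Protocol Table 3, footnote 2: "The clamp procedure will be considered as ended if the 20% GIR is on zero (0) and the infusion pump has been stopped", with the 12-hour mark as the alternative. Footnote 18 describes a clamp period "which will continue for up to 12 hours or until the GIR is 0 and blood glucose remains stable". Footnote 2 adds three further glucose readings for safety once the pump is at zero.
- **Sampling.** The synopsis ends the insulin and C-peptide lists with "180, 210, 240, 300, 600, and 720 minutes post-dose", and SAP Table 4.2 gives the same times. Protocol 13.1 ties sampling to dosing: "before and up to 12 hours after dosing for measurement of blood glucose, serum insulin, and C-peptide".

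The C-peptide data serve an exploratory aim, worded in SAP 2.3 as "To assess endogenous insulin suppression via C-peptide measurements". The endpoint in SAP 3.3 is corrected and uncorrected C-peptide concentrations. SAP 23.2 also uses C-peptide to correct the estimate of exogenous insulin.

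**The concern.** The fast ends with the clamp and the sampling ends with the clock. If the clamp stops early, the two come apart: a participant may eat and then give one or both of the late samples. C-peptide drawn after a meal reflects secretion stimulated by that meal, so it cannot be read as suppression of endogenous insulin by the study drug. A mean at 600 or 720 minutes could then pool fed and fasting values without anyone being able to tell them apart, because no passage asks for the meal time. The same values would enter the C-peptide correction of insulin at those times.

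**Working it through.** No figure in the plan has to be reproduced. The check sets the rules side by side and counts samples.

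1. **Sampling times after time 0** (synopsis; SAP Table 4.2): 5, 10, 20, 30, 40, 50, 60, 75, 90, 105, 120, 135, 150, 180, 210, 240, 300, 600, 720 minutes. That is 19 samples. Nothing is drawn between 300 and 600 minutes, so the last two are the only samples after 5 hours.

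2. **Can the clamp end before 720 minutes?** Yes. Footnotes 2 and 18 each give an early end as an alternative to 12 hours. The PD parameter tables (Protocol Table 6, SAP Table 23.2) list a GIR area to end of clamp separately from the area over 0-12 hours, which fits with the two end times being able to differ.

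3. **Samples that can follow the meal, by clamp-end time T:**
   - T = 720 minutes: none.
   - T between 600 and 720: the 720-minute sample only, 1 of 19.
   - T between 300 and 600: the 600- and 720-minute samples, 2 of 19.
   - T below 300: the 300-minute sample, and possibly earlier ones, could join them. The documents give no reason to expect this, so 2 of 19 is taken as the practical upper limit.

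4. **Illustration.** With T = 300 minutes, the late samples fall 600 - 300 = 300 and 720 - 300 = 420 minutes after clamp end. The three safety readings do not hold the fast to 600 minutes.

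5. **Does the SAP deal with such samples?** SAP 22.4 disregards only missing or non-reportable values. SAP 23.2 (C-peptide) and Section 24 (clamp procedure) say nothing about samples after clamp end or after eating. In Protocol Table 5 and SAP Table 22.2 the description of the 0-12 hour aspart area mentions end of clamp, but that is a PK parameter and not a rule for C-peptide.

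6. **How often?** The plan has 54 × 3 = 162 clamps at full enrolment. No distribution of clamp-end times is given, so the number affected could lie anywhere from 0 to 162.

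**The case against.** The strongest reply is that this is a 12-hour clamp. The design sections call it that, the Table 3 column heading says so, and glucose readings are scheduled to 720 minutes. Termination follows site SOPs that are not part of these documents, and the meal section does not say that food comes at once. The samples in question also come after GIR has reached zero, when little suppression would be left to measure. Finally, SAP 23.1 records the actual times of blood samples and GIR changes, so samples after GIR zero could be found later.

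Much of this stands. It shows that late samples can be post-meal, not that they will be, and that the loss of information on suppression is limited. It does not remove the gap. The footnotes expressly allow an early end, and GIR records do not give the meal time.

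A reader might infer four stronger things, which the documents do not support:

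- **That early ends would be routine**, because the Introduction puts the duration of action at 3-5 hours. That is a general statement. The plan's own duration of action runs from onset to half-maximal GIR on the way down, which comes before GIR zero, so 3-5 hours gives no clamp-end time.
- **That over a third of a C-peptide area is affected.** In a 0-12 hour trapezoid the two samples carry (300 + 120)/2 + 120/2 = 270 of 720 minutes, or 37.5%. No C-peptide area is planned, so this weight applies to no stated endpoint.
- **That the products would be biased against each other.** This needs their times to GIR zero to differ, and no data on that are given.
- **That the primary endpoints are contaminated.** No effect on them is shown. Any effect on the aspart area would depend on assay specificity, which Protocol 10.2 does not state.

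**Conclusion.** The concern holds as a minor inconsistency with a gap in the SAP. Following the plan as written, up to 2 of 19 post-dose C-peptide samples in a clamp that ends early can be post-meal, or 1 of 19 if it ends between 600 and 720 minutes. The SAP would summarize them together with fasting values. This assumes that the meal is given soon enough after clamp end to precede the next scheduled sample, and that no clamp ends before 300 minutes. The frequency cannot be derived. The consequence is confined to a descriptive exploratory endpoint and possibly to the C-peptide-corrected insulin values at the same times.

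**What to change.** **Protocol.** Reconcile Section 8.6.2.1 and Table 3 footnotes 2 and 18 with the sampling schedule in Table 4. How they are reconciled is a clinical decision for the sponsor and the investigator. Record the actual clamp-end time and meal time for each period.

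**SAP 23.2.** State that C-peptide suppression summaries use only samples drawn before the meal, or before clamp end where the meal time is not available. Show later values in listings only. Flag C-peptide-corrected insulin values that come from post-meal samples.

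**Cost.** A short clarification, two recorded times per period and a few SAP sentences. The price is fewer late C-peptide values in the summaries. Those kept would come from the clamps that ran longest, so the number contributing at 600 and 720 minutes should be shown by treatment.
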